PROSPECT is a prospective study of long-term outcomes in patients presenting with ACS. At baseline, 3-vessel angiography and intracoronary imaging with grayscale and RF-IVUS were performed to evaluate the characteristics of non-culprit lesions suspected to progress over time and cause major adverse cardiac events (MACE), defined as the composite of cardiac death, cardiac arrest, MI, unstable angina or increasing angina requiring re-hospitalization (7). By multivariable analysis, the only patient-level clinical variables independently associated with nonculprit lesion MACE during follow-up were insulin-treated diabetes and previous PCI (1). No angiographic variable was strongly associated with subsequent events. However, significant independent predictors of nonculprit lesion related MACE (i.e., events arising from those specific untreated lesions) were plaque burden $\geq 70\%$ (hazard ratio [HR]: 5.03; $p < 0.001$), the presence of a TCFA by RF-IVUS (HR: 3.35; $p < 0.001$), and a minimal lumen area $< 4.0 \text{ mm}^2$ (HR: 3.21, $p < 0.001$). The presence of 2 or 3 of these 3 characteristics identified lesions with a 10% and 18% likelihood, respectively, of an event arising from that site within 3 years (7). Conversely, the 3-year nonculprit lesion-related MACE rate in $>1,650$ IVUS lesions with none of these 3 characteristics was only 0.3%, and no events arose from coronary segments with $< 40\%$ plaque area.

A recent summary of the effort to detect and treat vulnerable plaque noted that in 5 separate studies, a large plaque burden by IVUS has been associated with an increased risk of progression to a MACE culprit lesion, thus establishing the principle that vulnerable plaques can be detected. (Madder, Muller, Journal of Interventional Cardiology, Supplement, 2013). However the specificity of the detection has not been adequate to serve as a guide to therapy. A more accurate measure of suspected vulnerable plaques is needed.

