6.2 SAMPLE SIZE CONSIDERATIONS

A total of 9,000 patients will be enrolled with multi-vessel scans. It is expected based on the PROSPECT Study that at least 720 patients (8%) will experience a NC-MACE event. We expect to find approximately 3,000 patients with large LRP (max 4mm LCBI \geq 250). All 3,000 of these patients will be followed with phone calls for 2 years to identify those who have an event. We expect to observe at least 300 events in this group. From the 6,000 with no or small LRP, a random sample of 3,000 patients will also be followed to determine their event rate, and to examine with IVUS and angiograms those in whom events occur. Of the approximately 2,700 patients with large LRP who do not have an event, a 300 person sample will be selected for IVUS and angiographic analysis to investigate characteristics of the yellow spots that did not lead to events.

Vulnerable Patient Analysis

For hypothesis 1, we will test the hypothesis that there will be no association between the baseline value of max 4mm LCBI (over the entire area scanned) and the incidence of NC-MACE.

In PROSPECT registry results, the 24-month cumulative incidence of NC-MACE in patients was approximately 10%. Subsequent STEMI literature indicates that patients with large LRP will have a higher rate than that observed in PROSPECT.

For the power calculations below, we assumed 6,000 evaluable patients, an event rate between 4 and 8% in the overall LRP study, and a two-sided alpha of 0.05 with a standard deviation of 100 for max 4mm LCBI. Table 2

provides values for the power of the study to detect the following effect sizes: hazard ratio of 1.18, 1.20, and 1.22 per 100 unit increase in max 4mm LCBI (calculated in PASS 12). These results demonstrate that the study will have 80% power to detect a minimal effect size of 1.18 per 100 unit increase in the max 4mm LCBI with 6,000 patients and an overall cumulative incidence of 5% at 24 months. As described in section 5.3, interim analyses will be performed at 6 month intervals.

Table 2: Hypothesis 1: Power Calculation for Vulnerable Patient Hypothesis

2 Year cumulative incidence overall, patient level	Relative Risk per 100 unit increase in max 4mm LCBI		
	1.18	1.20	1.22
8%	0.95	0.98	0.99
7%	0.92	0.96	0.98
6%	0.88	0.93	0.97
5%	0.82	0.88	0.93
4%	0.73	0.81	0.87

Vulnerable Plaque Analysis

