For hypothesis 2, we will test the hypothesis that there will be no association between the baseline value of max 4mm LCBI of the proximal, mid, or distal segment of a coronary artery and the incidence of NC-MACE.

For the vulnerable plaque analysis, we assumed that a patient will have a minimum of 50 mm of scanned target artery within at least 2 native epicardial arteries, yielding a minimum of 4 segments. Assuming that 24,000 segments (from 6,000 patients) will be available for analysis, a two sided alpha of 0.05 and a standard deviation of 100 LCBI units for max 4mm LCBI, Table 3 provides values for the power of the study to detect the following effect sizes: hazard ratio of 1.18, 1.20, and 1.22 (calculated by PASS 12). The study will have 80% power to detect a minimum effect size of 1.18 per 100 unit increase in the max 4mm LCBI with the minimum expected number of segments (24,000) and an overall cumulative incidence of 1.25% within the segments at 24 months.

Table 3: Hypothesis 2: Power Calculation for Vulnerable Plaque Hypothesis

2 Year cumulative incidence overall, segment level	Relative Risk per 100 unit increase in max 4mm LCBI		
	1.18	1.20	1.24
1.75%	0.92	0.96	0.98
1.50%	0.88	0.93	0.97
1.25%	0.82	0.88	0.93
1.00%	0.73	0.81	0.87
0.75%	0.60	0.69	0.76

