6.3 INTERIM ANALYSIS PLAN

As is evident from the power calculations provided in Section 5.2, for both the patient and segment level analysis, the LRP Study will have excellent power to detect relatively small increases in risk due to the presence of LRP.

The PROSPECT Study, with 700 patients, detected a hazard ratio of 5 for the presence of plaque burden > 70%. If the hazard ratio for increased LCBI reaches or exceeds 5, the LRP Study will provide definitive evidence that max 4mm LCBI predicts NC-MACE well before 6,000 patients have completed two-year follow-up. To provide an

opportunity for an early decision if this should occur, the LRP Outcomes Study will employ an interim analysis plan as described below.

When criteria for demonstrating an association between max 4mm LCBI and risk of NC-MACE have been met, the LRP Study will transition to a treatment study. This treatment study will include a control arm in which more detailed questions regarding the prognostic value of LCBI in various subgroups can be addressed in great detail.

The transition to a treatment study will require submission of a new protocol to the IRBs of the participating centers.

The interim analysis plan for the LRP Outcomes Study will be based on the Pocock spending function for repeated significance testing. This spending function will provide a greater opportunity for early stopping if strong associations emerge than would the O'Brien-Fleming or Haybittle-Peto spending functions. Specifically, review of accumulated data by the Data and Safety Monitoring Committee (DSMB) will occur on December 1, 2014 and at 6 month intervals thereafter until December 1, 2016. The DSMB will review the accumulated data to determine whether, in the multivariate analyses described in Section 5.1, both the vulnerable patient and the vulnerable plaque null hypotheses are statistically significant at the level required by the adjustment for repeated testing provided by the Pocock procedure. If those conditions are met, the DSMB may recommend termination of the study. If the study continues to the planned completion of two-year follow-up of all patients enrolled in the follow-up study, the two null hypotheses will be tested at the same significance level as that employed in the interim analyses. Additional information regarding the interim analysis plan will be provided in the Statistical Analysis Plan (SAP).

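### Section 6.3 allows an early stop on significance but states no adjustment of the reported hazard ratios and intervals for that stopping, and at the plan's own minimal effect they would overstate the association

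*Combined protocol and SAP*

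**What the plan says.** Section 6.3 (Interim Analysis Plan) schedules data reviews on 1 December 2014 and every six months until 1 December 2016. That makes five interim looks, followed by a final test at the same nominal level. The boundary is Pocock, chosen because it gives more chance of stopping early than the alternatives named there. The monitoring board checks whether both primary nulls are significant at that level in the multivariate models, and "If those conditions are met, the DSMB may recommend termination of the study". Meeting the criteria for an association also moves the programme to a treatment study under a new protocol.

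The section motivates the plan with a strong effect: "If the hazard ratio for increased LCBI reaches or exceeds 5, the LRP Study will provide definitive evidence that max 4mm LCBI predicts NC-MACE". The rule itself contains no hazard-ratio condition. Nothing in 6.3 says whether estimates or intervals after an early stop will be corrected for the stopping; further interim detail is left to the SAP.

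The effect the study is sized for is much smaller. Section 6.2 claims "80% power to detect a minimal effect size of 1.18 per 100 unit increase in the max 4mm LCBI with 6,000 patients", at 5% incidence.

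**The concern.** A Pocock boundary controls the error rate of the tests. It does not make the estimate at the stopping time unbiased. When the true effect is modest, the runs that cross early are those in which chance has pushed the estimate up, and an ordinary Cox hazard ratio and interval take no account of that selection.

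The reported hazard ratio is the quantity most likely to be carried forward. It will be read as the strength of the marker at patient and segment level, and it is the obvious starting value for planning the treatment study. An overstated figure would make the marker look more useful than the data support. The test of association would remain valid; the issue is the size attached to it.

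**Working it through.** **Inputs from the documents.** Section 6.2, H1: "a two-sided alpha of 0.05 with a standard deviation of 100 for max 4mm LCBI". A hazard ratio per 100 units is therefore a hazard ratio per SD. The same paragraph takes 6,000 patients as evaluable, of whom 4–8% have an event. Section 6.2, H2: "Assuming that 24,000 segments (from 6,000 patients) will be available for analysis"; at 1.25% incidence this is 24,000 × 0.0125 = 300 events, the same as 6,000 × 0.05 for H1. Section 5: enrolment from January 2014 to about December 2015, with 24 months of follow-up. Section 6.3: five looks plus a final test at one constant level.

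**Assumptions not in the documents.** The 6,000 followed patients accrue uniformly over 24 months; the hazard is constant; there is no loss to follow-up, reporting lag or variance inflation from covariates. The correlation between the H1 and H2 statistics is unknown and is varied.

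**Step 1: reproduce the plan's figure.** Power = Φ(√D × ln HR − 1.960) for a hazard ratio per SD. With D = 300 and ln 1.18 = 0.1655: √300 × 0.1655 − 1.960 = 0.907, and Φ(0.907) = 0.818. Table 2 prints 0.82. All 15 cells of Table 2 reproduce this way.

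**Step 2: smallest estimate that crosses.** The Pocock constant for six tests is 2.453 (nominal two-sided p about 0.014). An estimate crosses at look k if ln HR ≥ 2.453/√D_k. At 5% incidence:

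| Look | Month | Events D | 2.453/√D | Smallest HR | Ratio to ln 1.18 |
|---|---|---|---|---|---|
| 1 | 11 | 32 | 0.434 | 1.54 | 2.6 |
| 2 | 17 | 76 | 0.281 | 1.32 | 1.7 |
| 3 | 23 | 139 | 0.208 | 1.23 | 1.3 |
| 4 | 29 | 207 | 0.170 | 1.19 | 1.0 |
| 5 | 35 | 257 | 0.153 | 1.17 | 0.9 |

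With a true hazard ratio of 1.18, every stop at looks 1–3 must report more than the truth.

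**Step 3: simulate the joint rule.** Paths of both statistics were drawn with independent increments and true HR 1.18 for each hypothesis. A run stops when both first exceed 2.453. At 5% incidence:

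| | Correlation 0 | Correlation 0.5 |
|---|---|---|
| Stop at any interim look | 38% | 47% |
| Stop at look 1 | 0.4% | about 1.7% |
| Stop at look 1 or 2 | about 3% | about 7% |
| Mean reported HR over interim stops | 1.26 | 1.29 |
| Overstatement of log HR | about 38% | about 50% |
| Mean HR at look 1; look 2 | about 1.7; 1.4 | about 1.7; 1.4 |
| Naive 95% coverage at look 1; look 2 | about 60%; 85% | about 51%; 80% |

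**Step 4: range.** With perfect correlation at 5% incidence, an interim stop occurs in 64% of runs and log HR is overstated by about 59%. At 8% incidence, over correlations 0 to 1, an interim stop occurs in 71–85% and the overstatement is about 19–36%. A Lan-DeMets Pocock-type boundary gives similar stopping probabilities (40–65% at 5%, 72–86% at 8%).

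**Step 5: a strong true effect.** Section 4.2 expects one third of patients to have a large LRP. For a normal covariate, the top third and the rest differ in mean by 1.636 SD, so a binary hazard ratio of 5 is about 5^(1/1.636) = 2.7 per 100 units. At that value the joint rule stops at look 1 in over 99% of runs, with a mean estimate of about 2.7 and 95% coverage.

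**The case against.** The strongest reply has four parts.

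- **Early exaggeration is rare.** Requiring both nulls makes stops at looks 1–2 uncommon, and naive coverage over all runs stays at about 93–95%. This stands. Interval failure is confined to the early looks, and the general problem is an inflated point estimate.
- **It depends on a modest truth.** In the scenario that 6.3 describes there is nothing to correct. This also stands: a reader might infer that any early stop must exaggerate, and that is wrong.
- **There are safeguards.** The board may recommend but need not; Section 10.1 has it monitor the hazard ratio; the treatment study needs a new protocol and ethics review; nothing says the interim estimate will size that study. These limit the consequences but do not change the reported figure.
- **The SAP may deal with it.** Section 6.3 defers detail there, so its silence does not show that no correction is intended. The point is only that 6.3 states none.

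A reader might also infer that stopping should require a minimum effect, because 6.3 cites a hazard ratio of 5 and Section 2.1 says of IVUS that "the specificity of the detection has not been adequate to serve as a guide to therapy". The documents do not support that as an error. Sections 2.1.1, 3.1 and 6.1 make association the objective, 6.3 names association as its trigger, and the hazard ratio of 5 is a motivating case, not a threshold. A gate at the secondary cut of LCBI >400 would also be impractical: under a normal covariate with SD 100 and one third at or above 250, only about 2.7% of patients exceed 400. Delaying a stop while enrolment is open would also prolong research scanning as well as phone calls.

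**Conclusion.** The point holds as a reporting gap. Section 6.3 creates a substantial chance of stopping early at the effect the study is powered for, and does not say that the estimate will be adjusted. At a true hazard ratio of 1.18 and 300 events, an interim stop occurs in about 38–47% of runs, and the average reported value is 1.26–1.29. These figures rest on uniform accrual, constant hazard, equal effects for both hypotheses and a correlation of 0 to 0.5; the overstatement is smaller at 8% incidence.

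One related observation is worth recording without asking for a change to the rule. At looks 4–5 it can be met with a hazard ratio of about 1.13–1.19 per 100 units (1.17–1.19 at 5% incidence, 1.13–1.14 at 8%). For a normal covariate, AUC = Φ(ln HR/√2), which is about 0.53–0.55. An early stop therefore shows association, not useful discrimination. That is not peculiar to early stopping: the design effect of 1.18 itself corresponds to an AUC of about 0.55.

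**What to change.** Add to Section 6.3, with matching SAP text settled before the first look:

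- After any early stop, the patient-level and segment-level hazard ratios are reported with a selection-adjusted estimate and interval beside the naive Cox results.
- The method allows for the joint two-hypothesis rule, for example a median-unbiased estimate with stage-wise ordering extended to both statistics, or a simulation-based correction using their estimated correlation.
- The adjusted figure is the one used for any planning of the treatment study.
- An early stop is described as evidence of association; AUC and net reclassification are reported separately.

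The stopping rule, boundary and look dates stay as they are, and no effect-size condition is added. No extra data are needed. The cost is a little programming and analysis work, and a less favourable headline hazard ratio if the study stops early.

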7 ADVERSE EVENTS

The IVUS-NIRS TVC catheter is designed to function as a conventional, rotating core, IVUS catheter which has an excellent safety record. Experience with NIRS in over 5,000 patients has shown that the TVC catheter safety profile does not differ from that of a conventional IVUS catheter. Therefore the potential adverse events associated with the IVUS/NIRS in the additional, non-culprit vessels are expected to be similar to those of the culprit and include, at a very low rate (<1%):

- Additional radiation exposure
- Heart arrhythmias
- Cardiac tamponade
- Injury to the arteries
- Low blood pressure
- Bleeding
- Stroke
- Heart attack
- Death

7.1 UNANTICIPATED ADVERSE DEVICE EFFECT

Unanticipated Adverse Device Effect (UADE): An UADE is any serious adverse effect on health or safety, or any life threatening problem or death caused by, or associated with the device, if that effect, problem, or death is not identified in nature, severity, or degree of incidence in this IDE; or any other unanticipated serious problem associated with the device that relates to the rights, safety, or welfare of the subjects. (Significant device failure may constitute an adverse event if an undesirable experience occurs). This definition includes any event resulting

from insufficiencies or inadequacies in the instructions for use or the deployment of the device, or any event that is a result of a user error.

All UADEs should be documented on the appropriate Subject CRF documenting time of onset, a complete description of the event, severity, duration, actions taken and event outcome.

7.2 REPORTING SERIOUS ADVERSE EVENTS

The Investigator shall report all Adverse Effects, whether device related or not, to the Sponsor and to the reviewing IRB as soon as possible (per the overseeing IRB's policy), but in no event later than 10 working days after the Investigator first learns of the effect. The Investigator must determine if the adverse event is "serious." The regulatory definition of "serious" is an event that is fatal or life threatening, resulting in a persistent or significant disability, requiring intervention to prevent permanent impairment/ damage, or an event that results in congenital anomaly, malignancy, hospital admission or prolonged hospitalization. Anything the investigator deems to be serious MUST be reported to the Sponsor within one business day from the knowledge and determination of the event.

8 RISK/BENEFIT ANALYSIS

8.1 ANTICIPATED ADVERSE EFFECTS/ POTENTIAL RISKS FOR 2-3 VESSEL TVC SCANNING

The IVUS-NIRS TVC catheter is designed to function as a conventional, rotating core, IVUS catheter which has an excellent safety record. Experience with NIRS in over 5,000 patients has shown that the TVC catheter safety profile does not differ from that of a conventional IVUS catheter. Therefore the potential adverse events associated with the IVUS/NIRS in the additional, non-culprit vessels are expected to be similar to those of the culprit and include, at a very low rate (<1%):

- Additional radiation exposure
- Heart arrhythmias
- Cardiac tamponade
- Injury to the arteries
- Low blood pressure
- Bleeding
- Stroke
- Heart attack
- Death

8.2 POTENTIAL BENEFITS

A potential benefit of successful completion of this study for a patient with coronary artery disease is the demonstration that the NIRS-IVUS instrument can identify plaques that are at high-risk for rupture leading to a coronary event. If this phase of the study is positive, the next step will be to test novel local and/or systemic treatments to prevent the development of coronary events.

9 EXPENSE/REIMBURSEMENT TO SUBJECT

Subjects will not be reimbursed for participation.

10 MONITORING COMMITTEES

10.1 DATA SAFETY MONITORING COMMITTEE

The Data Safety Monitoring Committee (DSMC) will consist of one cardiologist and one bio-statistician with the remaining members to be announced. The purpose of the committee during the course of the trial will be to review accumulating safety data, to monitor the hazard ratio with regard to the Endpoints and other trends that would warrant modification or early termination of the trial.

The DSMC may request any data it deems necessary to review. The minimum frequency of DSMC meetings will be twice during the study period and to establish the charter prior to the first data review meeting. The DSMC may call a meeting at any time if there is a reason to believe there may be a safety issue with the study. The DSMC chairperson will notify the sponsor of the meeting conclusions by confidential memo of any needed communication.

Any DSMC recommendations for study modification or termination, because of concerns over patient safety or issues relating to data monitoring or quality control, will be submitted to the sponsor of the trial in writing for consideration and final decision. If the DSMC at any time determines that a potential serious risk exists to patients in this trial, the DSMC chairman will immediately verbally notify the Sponsor, followed by written notification of the concern.

10.2 CLINICAL EVENTS ADJUDICATION COMMITTEE

A Clinical Events Committee (CEC) consisting of at least three members will be established to review and adjudicate all clinical endpoints as defined in the protocol. The CEC will be independent from the study Sponsor. The primary mission of the Committee is to audit and review any major clinical event that occur within the follow up period for the purpose of accurate classification. The Committee will meet on an on-going basis as necessary to assure timely review of the data. Endpoint adjudication will be transmitted to the Data Analysis Center at MedStar for adjustment of the final database as necessary. The CEC will be blinded to all the Index IVUS-NIRS findings throughout the duration of the study.

11 INFORMED CONSENT

All subjects meeting the inclusion and exclusion criteria will be screened by the research staff and asked to give consent by a trained staff member. Subjects will be given ample time to consider participation in the trial.

In compliance with federal regulations governing informed consent, the informed consent form that is given to the subject or authorized representative must be in a language understood by the subject or his/ her legal representative. Prior to participation in the study, each subject must give written informed consent after having the study fully explained to him/her in the language that is most easily understood by the subject. All subjects must be given the opportunity to ask questions and to have those questions answered to his/her satisfaction. All informed consent forms must be approved by the IRB/EC before use and no subject may be consented unless such approval has been granted. All informed consent forms must be written in accordance with the current guidelines as outlined by GCP, ICH, and the Declaration of Helsinki (as applicable).

All informed consent forms must be signed and dated by the person providing explanation of the study and signed and dated by the subject or his/her legal representative prior to participation in this research study. A signed and dated copy of the informed consent form will be given to each subject.

